7.1.3.2 Oxaliplatin-Induced Pharyngolaryngeal Dysesthesia

Oxaliplatin can induce an acute syndrome of pharyngolaryngeal dysesthesia (grades 3/4) characterized by subjective sensations of dysphagia or dyspnea, feeling of suffocation, without any evidence of respiratory distress (no cyanosis or hypoxia) or of laryngospasm or bronchospasm (no stridor or wheezing) occurs in 1-2% of the patients.

If a patient develops this oxaliplatin-induced pharyngolaryngeal dysesthesia, proceed to evaluate the oxygen saturation with a pulse oximeter and if confirmed as normal, an anxiolytic agent may be given and the patient observed in clinic until the episode has resolved. The duration of the oxaliplatin infusion should be increased to six hours for all subsequent treatment cycles.

Pharyngolaryngeal dysesthesia may appear similar to a hypersensitivity reaction. The table below compares the two.

Comparison of the symptoms and treatment of pharyngolaryngeal dysesthesias and platinum hypersensitivity:

Clinical Symptoms	Pharyngolaryngeal dysesthesias	Platinum hypersensitivity
Dyspnea	present	present
Bronchospasm	absent	present
Laryngospasm	absent	present
Anxiety	present	present
O ₂ saturation	normal	decreased
Difficulty swallowing	present (loss of sensation)	absent
Pruritis	absent	present
Urticaria/rash	absent	present
Cold-induced symptoms	yes	no
Blood pressure	normal or increased	normal or decreased
Potential treatments	anxiolytics, observation in a controlled clinical setting until symptoms abate or at the physician's discretion	oxygen, steroids, epinephrine, bronchodilators; fluids and vasopressors, if appropriate

7.1.3.3 CAPOX

The precise dose modification schema used and the symmetry of dose modification may be left to the discretion of the treating oncologist. The modification schema in Table Dose levels of CAPOX is a guideline.

CAPOX Dose Levels for NON-neurologic toxicity:

Dose Level*	Oxaliplatin	Capecitabine
0	130 mg/m ²	1000 mg/m ² bid
-1	100 mg/m ²	750 mg/m ² bid
-2	85 mg/m ²	500 mg/m ² bid
-3	Discontinue Therapy	Discontinue Therapy

* Dose level 0 refers to the starting dose.

Suggested CAPOX Dose Modifications Based on Interval Adverse Events

SYSTEM/ORGAN/CLASS (SOC)	ADVERSE EVENT	AGENT	DOSAGE CHANGE
BASED ON INTERVAL ADVERSE EVENT (Occurring before Day 11 -14 of Cycle)			
Blood and lymphatic Systemic disorders	Neutropenia ANC (x 10 ⁹ /L) 1000-1199	Capecitabine Oxaliplatin	If ANC less than 1.2 on Day 1 of cycle, hold treatment. Perform weekly CBC, maximum of 2 times. If ANC is greater than or equal to 1.2 within 2 weeks, proceed with treatment at the dose level noted across from the lowest ANC result of the delayed week(s). If ANC remains less than 1.2 after 2 weeks, discontinue treatment.
	ANC (x 10 ⁹ /L) 500 - 999		Follow steps in first box above and if resumed, with one dose level reduction.
	ANC (x10 ⁹ /L) less than 500		Follow steps in first box above but resume with two dose level reduction.
	Platelets (x 10 ⁹ /L) 50 – 74.9	Capecitabine Oxaliplatin	If platelets less than 75 on Day 1 of cycle, hold treatment. Perform weekly CBC, maximum of 2 times. If platelets greater than or equal to 75 within 2 weeks, proceed with treatment at the dose level noted across from the lowest platelets result of the delayed week(s). If platelets remain less than 75 after 2 weeks, discontinue treatment.
	Platelets (x 10 ⁹ /L) 10 – 49.9		Follow steps in first box above and if resumed, with one dose level reduction from the lowest platelets result of the delayed week(s).
	Platelets (x 10 ⁹ /L) Less than 10.0		Follow steps in first box above but resume with two dose level reduction from the lowest platelets result of the delayed week(s).

The following describe actions in the Dosage Change column:

- Omit = Treatment is not given for this cycle
- Hold = Treatment can be made up as part of this cycle
- Discontinue = Treatment is totally stopped

7.1.4 Duration of Therapy

In the absence of unacceptable toxicities or disease progression, as defined in Section 10.1, or intolerable toxicity, chemotherapy will continue until completion of 6 cycles for FOLFOX and 4 cycles for CAPOX.

7.1.5 Patient Compliance

Trained medical personnel will administer protocol chemotherapy. Treatment compliance will be recorded in the patient's medical record and case report form (CRF).

Capecitabine treatment compliance will be monitored by review of the patient diary.

7.2 Radiation Treatment Plan

Pelvic radiation is recommended for patients when the excisional specimen demonstrates ypT3+ or N+ disease and requires radical TME surgery. Patients should be treated with standard preoperative chemoradiation or short course pelvic radiation according to standard institutional pre-operative protocol.

Optional preoperative pelvic radiation could be delivered as per institution standard to patients with pre-excision MRI reporting at least one of these findings:

- cT3^{ab} stage
- node positive disease
- not clear circumferential radial margin (CRM)

Patients with yp staging as T1 (high risk) and T2 tumours do not require pre-operative pelvic radiation and should proceed directly to radical TME surgery.

Patients who cannot tolerate six cycles of FOLFOX or those that require dose modification below dose level -2 (see Section 7.1.3.1) may receive preoperative 5FU chemoradiotherapy based on investigator decision. If chemoradiotherapy is given, it should be given according to local institutional guidelines for FOLFOX administration.

7.3 Surgical Treatment Plan

Tumour excision should be performed within 2-5 weeks (FOLFOX) or 3-6 weeks (CAPOX) after first dose of last cycle of chemotherapy.

Step/Indication	Result	Surgical Treatment Plan
Pre-excision MRI/Endoscopy (post-chemotherapy)	
 • Disease Progression OR • No Response demonstrated by at least one of these findings on pre-excision MRI 
 - cT3^{ab} stage - node positive disease - not clear circumferential radial margin (CRM) 	Total Mesorectal Excision (TME) or optional radiotherapy (per institution standard) followed by TME
	
 • No Disease Progression • Pre-excision MRI not meeting the “no response” criteria 	TAMIS/TEMS
TEMS/TAMIS	
yp Staging :
 
 • ypN+ OR • ypT3 	Radiotherapy (per institution standard) followed by TME
	
yp Staging:
 
 • ypT2 OR • ypT1 tumours with: 
 - poorly differentiated histology and/or - lymphovascular invasion and/or - positive margin within < 1 mm 	TME
	
yp Staging:
 
 • ypT0 N0 • ypT1^{good} N0 	Surveillance

Lesions that on pre-excision (post-chemotherapy) MRI and/or endoscopy show evidence of progression or no response to chemotherapy (see protocol section 8.2) should be treated with immediate TME surgery as progression of local disease in spite chemotherapy is an established poor prognostic factor.

Local pathology ypstaging review determines subsequent therapy. Patients with ypstage T0/T1^{good}N0 tumours are treated with surveillance while patients with tumours with ypT2, N+ or ypT1 tumours with poor prognostic features or are treated with radical TME surgery within 6-8 weeks after local excision. Poor prognostic features include poorly differentiated histology, lymphovascular invasion and/or positive margin within < 1 mm. ypT1^{good} are those tumours that do not have poor prognostic factors.

For information about retrospective ypstaging confirmation by central pathology review refer to section 11.1 of this protocol.

Surgeons performing TEMS/TAMIS in this trial should have performed these procedures in at least 20 previous rectal cancer cases [*Stevenson 2015; Bonjer, 2015; Fleschman, 2015*]. Each surgeon should submit an unedited video of a TEMS/TAMIS procedure with sutured defect closure for central review. A video of the 1st patient enrolled in CO.28 is acceptable.

Surgeon trainees are not excluded from performing TME but their cases must be performed under supervision of a qualified surgeon and cancer-specific surgery must be ensured.

As per protocol, transanal, endoscopic tumour excision is permitted for low rectal tumours that approach or involve the anal sphincter if complete excision is feasible.

Lesions that on pre-excision (post-chemotherapy) MRI and/or endoscopy show evidence of progression or no response to chemotherapy (see protocol Section 8.2) should be treated with immediate TME surgery as progression of local disease in spite chemotherapy is an established poor prognostic factor.

Prior to surgery, all patients will have pretreatment with mechanical bowel preparation, with the specific bowel cleansing regimen at the discretion of the treating surgeon. Patients will be usually admitted to hospital on the day of surgery. Appropriate antibiotics for gram positive, negative and anaerobic coverage, and taking patient allergies/sensitivities into considerations will be administered as per institutional guidelines preoperative or at the start of the procedure. Heparin will not be administered.

The operating surgeon will use the minimally invasive transrectal platform of their choice. If the tumour encroaches into the anal canal, the surgeon can start the procedure using conventional transanal technique and complete the procedure with the transanal platform inserted using minimally invasive techniques. Where possible, the procedure will be video recorded. Excision of the tumour will include a minimum of 1 cm gross margin [*Monson et al. 2013*], and a full thickness rectal excision, including a cuff of mesorectal fat. [*Lezoche 2012*]. After specimen extraction, vigorous irrigation with water will be recommended to minimize the risk of tumour implantation. The preferred management of the rectal defect will be sutured closure.

If the tumour has progressed and is no longer appropriate for local excision, the surgeon will photodocument the lesion and abandon the procedure.

The surgical specimen will be pinned to a cork board to prevent distortion of the orientation and photographed. The specimen will be reviewed by pathology for ypstaging.

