7.7 Efficacy

7.7.1 Organ Preservation Rate

After completion of neoadjuvant chemotherapy, the protocol requires that patients with lesions that on pre-excision (post-chemotherapy) MRI and/or endoscopy showing evidence of progression or no response to chemotherapy to be treated with immediately

the radical TME surgery. Other patients will be treated with local excision TEMS or TAMIS. Patients with ypstage T0/T1goodN0 tumours based on local pathology ypstaging review after TEMS or TAMIS are treated with surveillance while patients with tumours with ypT2, N+ or ypT1 tumours with poor prognostic features are treated with radical TME surgery within 6-8 weeks after local excision. The numbers of enrolled patients who were treated with respectively neoadjuvant chemotherapy, TME and TEMS or TAMIS immediately after completion of neoadjuvant chemotherapy, and TME or surveillance after TEMS or TAMIS will be summarized (**Table 30**).

Organ preservation rate, the primary endpoint of this study, is defined as the proportion of patients with tumour downstaging to ypT0/T1good N0 who avoid radical surgery (TME) among all patients treated with FOLFOX or CAPOX and TEMS or TAMIS. The 95% confidence interval for the organ preservation rate will be calculated (**Table 30**).

Organ preservation rate will additionally be calculated among all patients that have received neoadjuvant chemotherapy.

7.7.2 3 Year Loco-Regional Relapse Rate

Locoregional relapse is defined as reappearance of a tumour within the rectum or pelvis. The number of patients with each site (rectum, pelvis, pelvic lymph nodes, and others) of locoregional relapse will be summarized (**Table 31**).

Locoregional relapse free survival is calculated as time from complete tumour surgical excision date (with pathology results negative for malignant disease within 1 mm of surgical margins) to the first date of definitive evidence (clinical, radiological or pathological) of locoregional relapses. Patients with distant relapse only, died, loss to follow up, or alive at clinical cut-off will be censored at respectively last date of distant relapses, date of death, date of lost to follow-up, and last disease assessment date calculated as the last of dates of attendance/last contact on Follow-up Report.

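### Protocol and SAP give inconsistent instructions on radiotherapy before TME, both for progression or no response before excision and for node-positive excision specimens

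*Protocol*

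**What the plan says.** **Progression or no response before excision.** Protocol 7.2 says: "Optional preoperative pelvic radiation could be delivered as per institution standard to patients with pre-excision MRI reporting at least one of these findings". The findings are cT3ab stage, node-positive disease and a circumferential radial margin that is not clear. The 7.3 table, for disease progression or any of those findings, lists TME or, as an option, "radiotherapy (per institution standard) followed by TME". The narrative below that table, and again later in 7.3, says that lesions showing progression or no response "should be treated with immediate TME surgery as progression of local disease in spite chemotherapy is an established poor prognostic factor". SAP 7.7.1 restates this as something the protocol requires.

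**Excision specimen.** Protocol 7.2 says: "Pelvic radiation is recommended for patients when the excisional specimen demonstrates ypT3+ or N+ disease and requires radical TME surgery". It allows either preoperative chemoradiation or short-course radiation. The 7.3 table has one row for ypN+ or ypT3 (radiotherapy, then TME) and another for ypT2 or poor-risk ypT1 (TME). For high-risk T1 and for T2, 7.2 says that patients "do not require pre-operative pelvic radiation and should proceed directly to radical TME surgery", with no condition on nodal status. The 7.3 narrative groups the findings differently: "patients with tumours with ypT2, N+ or ypT1 tumours with poor prognostic features or are treated with radical TME surgery within 6-8 weeks", counted from the local excision. That sentence contains a stray conjunction, so words may have been lost. SAP 7.6 repeats the recommendation in 7.2. SAP 7.7.1 repeats the narrative: the same group "are treated with radical TME surgery within 6-8 weeks after local excision".

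**Analysis rules that depend on this.** Protocol 8.7 and SAP 7.7.4 count non-protocol radiotherapy without a documented site of failure as a DFS failure. SAP 7.6 promises a summary of any pelvic radiation given before TME, reported in Table 29.

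**The concern.** A site that follows the 7.3 table and a site that follows the narrative beneath it can treat the same finding differently, and each can point to written text. The SAP does not settle the matter, because 7.6 carries one version and 7.7.1 the other.

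Three things are at stake. First, avoiding the toxicity of pelvic radiation is part of the trial's rationale (Protocol 2.0), so unclear radiotherapy use makes complications, toxicity, quality of life, relapse and DFS harder to interpret among patients who go on to TME. Second, deviation coding has no single standard to code against. Third, the DFS definition turns on whether radiotherapy was protocol or non-protocol treatment, and neither document lists which radiotherapy is which.

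**Working it through.** **1. The instructions side by side**

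| Finding | Protocol 7.2 | Protocol 7.3 table | Protocol 7.3 narrative | SAP |
|---|---|---|---|---|
| MRI no response | Radiotherapy optional | TME, or optional radiotherapy then TME | Immediate TME (twice) | 7.7.1: immediate TME |
| Progression | Not in the list | TME, or optional radiotherapy then TME | Immediate TME (twice) | 7.7.1: immediate TME |
| ypN+ | Radiotherapy recommended | Radiotherapy then TME | TME within 6-8 weeks, radiotherapy not mentioned | 7.6 as Protocol 7.2; 7.7.1 as narrative |
| ypT3 | Radiotherapy recommended | Radiotherapy then TME | Not listed | 7.6 as Protocol 7.2; 7.7.1 does not list it |
| ypT2 N+ | Fits both the N+ and the T2 sentence | Fits both rows | TME within 6-8 weeks | Same split |

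For progression or no response, an option and an immediate operation are different instructions. For N+, the difference lies in grouping and silence: the narrative does not mention radiotherapy, but it does not rule it out either.

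**2. The 6-8 week window.** This is a rule, so there is no calculated figure to reproduce. The documents give no radiotherapy duration, no lag from excision to radiotherapy and no interval from radiotherapy to TME. As an illustration on assumed values (lag 2 to 4 weeks; radiotherapy 1 week for a short course, 5 to 6 weeks for chemoradiation):

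weeks left = window limit − lag − duration

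- Short course, lag 2: 6−2−1 = 3 to 8−2−1 = 5 weeks left.
- Short course, lag 4: 6−4−1 = 1 to 8−4−1 = 3 weeks left.
- Chemoradiation of 5 weeks, lag 2: 6−2−5 = −1 to 8−2−5 = 1 week left.
- Chemoradiation of 6 weeks, lag 4: 6−4−6 = −4 to 8−4−6 = −2 weeks left.

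On these assumptions a short course can fit, while chemoradiation leaves at most 1 week and usually overruns. What the documents do show is that one window is stated for N+ patients, with no timing for those irradiated first.

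**3. DFS.** The clock starts at complete excision with clear margins (Protocol 8.7, SAP 7.7.4).

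- *First TME after no response.* Radiotherapy comes before TME, so it precedes time zero and cannot be a DFS event. These patients are also outside the main DFS set, which requires TEMS or TAMIS; they enter only the additional analysis of all chemotherapy-treated patients.
- *N+ or ypT3 after a clear-margin TEMS/TAMIS.* The local excision can itself meet the time-zero definition. Radiotherapy before the later TME would then fall after time zero, in a patient who belongs to the main DFS set. Whether it could be counted depends on the unstated line between protocol and non-protocol radiotherapy.

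**4. Table 29.** SAP 7.6 covers any pelvic radiation before TME. Table 29 uses the Chemotherapy & Excision set, which SAP 6 defines by TEMS or TAMIS. A non-responder irradiated and then given TME as the first operation would be missing.

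**5. Primary endpoint.** Every planned pathway in dispute ends in TME. N+ patients after TEMS/TAMIS stay in the denominator as failures either way. Patients whose first operation is TME are outside the primary set either way, and count as failures in the additional chemotherapy-treated rate either way.

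**The case against.** The strongest reply is that most of this is looseness rather than contradiction. For N+, three places (Protocol 7.2, the 7.3 table, SAP 7.6) agree on radiotherapy before TME. The narrative sits in a surgical section and mainly separates surveillance from TME. That is fair: a reader might infer that the narrative forbids radiotherapy for N+, and the text does not say so. The mismatch in grouping, the missing ypT3 and the ypT2 N+ overlap remain.

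For non-responders, immediate TME could mean TME without a prior local excision, since SAP 7.7.1 contrasts it with TEMS/TAMIS. Radiotherapy is also expressly optional and left to institutional standard, so some variation between like patients is intended and would remain under a consistent text. Both points have weight. Even so, immediate sits badly with an optional course of radiotherapy beforehand, and SAP 7.7.1 presents it as a requirement.

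On DFS, radiotherapy written into the protocol's own radiation plan looks like protocol treatment on its face, and the event also requires that no site of failure is documented. This narrows the question to radiotherapy after a clear-margin TEMS/TAMIS, but a definition is still missing.

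Finally, SAP 2.2 records that accrual closed on May 19, 2020, so a clarification may come too late to change care for most patients. Deviation coding and the final analysis still depend on it.

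**Conclusion.** The instructions are inconsistent as written and need reconciling. The conflict is direct for progression or no response. For N+ specimens it is a mismatch of grouping and an omission, with ypT2 N+ falling in two rows and no timing given after radiotherapy.

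The effect on the primary endpoint and the two-stage decision is nil, provided that patients follow the planned pathways. The effect on secondary outcomes cannot be sized, because the documents do not say how many of the 58 accrued patients had these findings. Protocol 2.0 notes that local excision cannot clear the nodes completely, so N+ may seldom be found in an excision specimen.

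Two stronger readings go beyond the documents. One is that the 6-8 week window cannot accommodate radiotherapy: short course is allowed and no durations are stated, so this rests on assumption. The other is that radiotherapy before a first TME would be scored as a DFS failure: it precedes time zero. This review takes no view on which clinical rule is right.

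**What to change.** 1. The sponsor's clinical team should reconcile Protocol 7.2, the 7.3 table, both statements in the 7.3 narrative, SAP 7.6 and SAP 7.7.1 into one instruction per finding. This should cover progression, MRI no response, N+, ypT2 N+ and ypT3, and state the TME timing for patients irradiated first.
2. Before the final analysis, SAP 7.7.4 should state that radiotherapy given under Protocol 7.2 is protocol treatment and is not a non-protocol radiotherapy event for DFS.
3. The data set for Table 29 should be aligned with SAP 7.6, so that patients irradiated before a first TME are included.

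The cost is a protocol clarification and SAP wording, plus one changed table population. No change to sample size or to the primary analysis is needed.

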7.4 Concomitant Therapy

7.4.1 Permitted

Use of G-CSF (Gastrofil, Neulasta or Neupogen) is at the discretion of treating physicians but is not usually necessary.

7.4.2 Not Permitted

Erythropoietin stimulating agents should not be administered at any point during this protocol.

8.0 CRITERIA FOR MEASUREMENT OF STUDY ENDPOINTS

8.1 Definitions

8.1.1 *Evaluable for Organ Preservation Rate*

All patients treated with FOLFOX or CAPOX and TEMS or TAMIS will be included in the organ preservation rate analysis as primary endpoint of this study.

Organ preservation rate will additionally be calculated for all patients that have received protocol chemotherapy.

8.1.2 *Evaluable for Rectal Cancer Control*

All patients treated with FOLFOX or CAPOX and TEMS or TAMIS will be evaluated for locoregional and distant relapse rate.

Rectal cancer control will additionally be calculated for all patients that have received protocol chemotherapy.

8.1.3 *Evaluable for Disease Free Survival*

All patients treated with FOLFOX or CAPOX and TEMS or TAMIS will be evaluable for assessment of disease free survival.

Disease Free Survival will additionally be calculated for all patients that have received protocol chemotherapy.

8.1.4 *Evaluable for Post-Operative Complications*

All patients treated with FOLFOX or CAPOX and tumour excision/surgery will be evaluable for post-operative complications.

8.1.5 *Evaluable For Adverse Events*

All patients who have received at least one dose of protocol chemotherapy will be included in the safety analysis.

8.1.6 *Evaluable for Quality of Life Assessment*

All patients who have completed a quality of life questionnaire are evaluable for quality of life.

8.2 *Evidence of Disease Progression/No Response After Chemotherapy*

8.2.1 *Progression*

The diagnosis of progressive disease will be made by treating surgeon after review of the pre-excision (post-chemotherapy) MRI and endoscopy.

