The shortened duration of induction FOLFOX chemotherapy proposed by this study reduces toxicity and is similar in duration to the ongoing phase III CRC.7 “PROSPECT” study to evaluate the role of induction chemotherapy as a means to avoid pelvic radiation. Pathologic stage after induction therapy (ypStage) remains the strongest and most consistent prognostic factor in rectal cancer and allows the safe stratification to observation after minimally invasive surgery or to radical surgery for those with ypT2 or higher stage tumours. The combination of reduced local recurrence and less radical surgery will substantially benefit patients while decreasing surgical and hospital resources and complications. The NEO Trial builds on the concept established by CRC.7 of neoadjuvant FOLFOX chemotherapy without pelvic irradiation as an experimental treatment for early rectal tumours.

Radical surgery for invasive rectal cancer aims to remove the primary tumour and locoregional nodes and tumour deposits. While local excision can successfully remove the primary tumour, complete nodal clearance is not possible with this technique. The role of neoadjuvant chemotherapy is to treat locoregional tumour spread and improve locoregional tumour control. In table I, the frequency of pathologic node involvement in cT1-3 tumours is summarized, and both standard and exploratory treatment approaches are listed.

Table 1. Pathologic node involvement (pN+) in cT1-3 tumours, with standard and exploratory treatment approaches.

Clinical Stage	pN+Rate	Standard Treatment	Exploratory Therapy
cT1N0	11-15%	TME	Excision/TEMS/TAMIS in low risk
cT2N0	22-28%	TME	Chemoradiation + TEMS = Chemoradiation + TME post (Randomized Phase II)
cT3N0	>30%	ChemoRT + TME	“Watch & Wait”: multiple retrospective case series report a 50% organ preservation rate among patients with cT3+ tumours with a clinical response to induction chemoRT +/- chemotherapy.

[Verseveld 2015; Perez 2014; Minsky 1989; Brodsky 1992; Salinas 2011; Lezoche 2012; Habr-Gama 2013]
 Abbreviations: c: clinical; pN+: pathologic node positive; TME: total mesorectal excision (radical surgery); LE: local excision; ChemoRT: chemoradiation; TEMS: transanal excisional microsurgery.

T1N0 Tumours

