Neurological	Neurotoxicity grade 2 persisting between treatment cycles	Oxaliplatin	Continue FOLFOX with previous dose level of 5-FU and one dose level reduction of oxaliplatin for all subsequent cycles.
	Neurotoxicity grade 3 resolving to \leq grade 2 between treatment cycles		Continue FOLFOX with previous dose level of 5-FU and one dose level reduction of oxaliplatin for all subsequent cycles.
	Neurotoxicity grade 3 persisting between treatment cycles		Discontinue oxaliplatin. Continue 5-FU/leucovorin. Reassign to 5FUCMT if has not completed at least 5 cycles of FOLFOX.
	Neurotoxicity grade 4		Discontinue oxaliplatin. Continue 5FU/leucovorin. Reassign to 5FUCMT if has not completed at least 5 cycles of FOLFOX.
Cardiovascular	Cardiac ischemia or infarction grade 3 or 4		Discontinue all study therapy.
	Cerebrovascular ischemia grade 3 or 4		Discontinue all study therapy.

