8.3 Organ Preservation Rate

Organ preservation rate is defined as the proportion of patients who avoid TME.

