4.3 Safety

The safety endpoints are post-operative complication rate, serious and non-serious adverse events (clinical and laboratory), laboratory parameters, dosing data (including dose interruptions, total delivered dose and dose modifications) and reasons off treatment.

5. Sample Size and Power

The expected organ preservation rate is 50-68% among patients with clinical T1-3N0 rectal tumours treated with chemoradiation and minimally invasive surgery. Based on these historic phase II data, the experimental treatment would be considered of no interest if the protocol specified organ preservation rate is 50% or lower (H_0) and as promising if its avoidance rate is 65% or higher (H_1).

An optimal two-stage minimax design would be used to test the above hypotheses, which would accrual 22 evaluable patients in the first stage. The trial would be stopped at the end of the first stage if the number of patients who avoided radical surgery is 10 or less. Otherwise the trial would proceed to the second stage to accrue 28 additional evaluable patients. The experimental procedure would be considered as promising if, out of the total patients accrued, 30 or more patients avoided radical surgery. The exact type I error rate and power of this design are respectively 0.1 and 0.8. Allowing for a 15% inevaluable rate, the total sample size would be 58 patients.

6. Data Set Descriptions

Five types of analysis samples will be used:

1. All Accrued Patients:

All patients accrued in the study.

2. All Chemotherapy Treated Patients:

All patients who have received at least one dose of FOLFOX or CAPOX.

3. All Chemotherapy & Excision Treated Patients

All patients who have received at least one dose of FOLFOX or CAPOX and TEMS or TAMIS.

4. All Chemotherapy & Excision/Surgery Treated Patients

All patients who have received at least one dose of FOLFOX or CAPOX and excision (TEMS or TAMIS) or surgery (TME).

5. All Quality of Life Evaluable Patients

All patients who have completed at least one quality of life questionnaire.

7. Statistical Analysis

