7.6 Radiation Treatments

Pelvic radiation is recommended for patients when the excisional specimen demonstrates ypT3+ or N+ disease and requires radical TME surgery. The following information will be summarized for patients who received any pelvic radiation therapy prior to TME surgery:

- Site of Radiotherapy: Rectum, Sigmoid colon, Anus (**Table 29**)
- Duration of Radiotherapy (days): median, minimum, maximum (**Table 29**)
- Total dose of radiation: median, minimum, maximum (**Table 29**)

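### The primary organ preservation set and numerator carry no radiotherapy condition, so a patient given the permitted chemoradiotherapy and then TEMS/TAMIS is not excluded and would count as a success of chemotherapy without radiation

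*Protocol*

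**What the plan says.** **Who is analysed.** Protocol 8.1.1: "All patients treated with FOLFOX or CAPOX and TEMS or TAMIS will be included in the organ preservation rate analysis as primary endpoint". SAP section 6, data set 3, sets the chemotherapy requirement at a single dose: "All patients who have received at least one dose of FOLFOX or CAPOX and TEMS or TAMIS".

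**What counts as success.** Protocol 8.3: "Organ preservation rate is defined as the proportion of patients who avoid TME". Protocol 13.2 and SAP 7.7.1 add downstaging. The SAP counts patients with "ypT0/T1good N0 who avoid radical surgery (TME) among all patients treated with FOLFOX or CAPOX and TEMS or TAMIS". Neither form has a radiotherapy condition. The additional rate over all chemotherapy-treated patients has none either.

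**Where radiotherapy can enter before excision.** Under Protocol 7.1.1.1 note 3, repeated in 7.2, patients who cannot tolerate six FOLFOX cycles, or who need a dose below level -2, "may receive preoperative 5FU chemoradiotherapy based on investigator decision". The neurological rows of the FOLFOX dose table in 7.1.3.1 say "Reassign to 5FUCMT if has not completed at least 5 cycles of FOLFOX". The abbreviation is not defined; I read it as 5FU combined-modality therapy, which is an assumption.

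**What the trial is meant to test.** Protocol 2.0 describes the concept as "neoadjuvant FOLFOX chemotherapy without pelvic irradiation as an experimental treatment for early rectal tumours". The 50-68% benchmark in Protocol 13.3 comes from chemoradiation plus minimally invasive surgery.

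**What is reported.** The text of SAP 7.6 summarises radiotherapy "for patients who received any pelvic radiation therapy prior to TME surgery". Table 30, which carries the primary result, has no radiotherapy row.

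**The concern.** Take a patient who stops FOLFOX early for toxicity, receives pelvic chemoradiotherapy, has a satisfactory MRI and endoscopy, and then has TEMS with ypT0 N0. Read literally, the definitions place this patient in the primary set and in the numerator. Yet the treatment received is close to the chemoradiation approach that supplied the historical benchmark. The success would be credited to a strategy whose rationale is to avoid pelvic radiation.

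What is at stake is the meaning of the primary rate and, near the cut-off of 30 of 50, the verdict. The issue is how such patients are counted and displayed. It is not which clinical route they should follow.

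**Working it through.** **1. Does the text close the path?** Setting the sections side by side:

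- Protocol 7.1.1.1 note 3 and 7.2 permit preoperative chemoradiotherapy after FOLFOX intolerance. The operation is not named.
- Protocol 7.1.3.1 asks the investigator to consider TME referral if the dose falls below level -2 in cycles 1-5, or after a toxicity hold of more than 30 days. Its table footnote, for the dose criterion, refers the patient to standard surgical therapy.
- Protocol 7.3 routes to TEMS/TAMIS on the pre-excision MRI and endoscopy alone, with no exclusion for prior radiation. Its excision window runs from the last chemotherapy cycle, and it gives no window after chemoradiotherapy.
- The other preoperative radiation route, for MRI non-response, ends in TME under 7.3. Those patients fail the endpoint and cause no problem.
- No equivalent permission is written for CAPOX.

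The gap is therefore the FOLFOX-intolerance route only. The sequence of chemoradiotherapy then TEMS/TAMIS is not prescribed, but neither is it excluded.

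**2. Reproduce the design (Protocol 13.3).** Inputs: 22 patients in stage 1, stop at 10 or fewer; 28 more; promising at 30 or more of 50.

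P(promising | p) = sum over x = 11 to 22 of P(X1 = x) × P(X2 ≥ 30 − x), with X1 ~ Bin(22, p) and X2 ~ Bin(28, p).

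| p | P(promising) | Protocol |
|---|---|---|
| 0.50 | 0.0977 | 0.1 |
| 0.65 | 0.802 | 0.8 |

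P(X1 ≤ 10 | 0.50) = 0.416, against the stated 42%. The design figures are right and are not in dispute.

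**3. Effect of counting irradiated patients as eligible successes.** The documents give no switch rate, so f is assumed to be 2%, 5% or 10% of the evaluable set (1 to 5 patients of 50). Let s be the success rate of irradiated patients, taken from the 50-68% benchmark, and let the others succeed at the null rate of 0.50. The overall rate is a mixture:

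p = (1 − f) × 0.50 + f × s

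| f | s = 0.50: p | P(promising) | s = 0.68: p | P(promising) |
|---|---|---|---|---|
| 2% | 0.500 | 0.098 | 0.5036 | 0.107 |
| 5% | 0.500 | 0.098 | 0.5090 | 0.121 |
| 10% | 0.500 | 0.098 | 0.5180 | 0.149 |

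**4. Effect of counting them as non-successes while keeping the 30-of-50 rule.** The rate becomes (1 − f) × 0.65 under the alternative and (1 − f) × 0.50 under the null.

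| f | Rate under alternative | Power | Rate under null | Type I error |
|---|---|---|---|---|
| 2% | 0.637 | 0.745 | 0.490 | 0.075 |
| 5% | 0.6175 | 0.646 | 0.475 | 0.050 |
| 10% | 0.585 | 0.463 | 0.450 | 0.023 |

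**5. Would the tables reveal these patients?** Table 29 is headed with the chemotherapy-and-excision set, and its first row counts patients with radiation, with no TME limit in the shell. As drawn, it would mix radiation before TEMS/TAMIS with radiation given between TEMS/TAMIS and TME for ypT3 or N+ disease. Table 47 has a radiotherapy row for other anti-cancer treatment during protocol treatment. Neither is cross-tabulated with organ preservation.

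**The case against.** Four points can be made for the plan.

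- **The pathway is inferred.** No section says TEMS/TAMIS follows chemoradiotherapy, 7.1.3.1 points part of this group to TME or standard surgery, and 7.3 describes no assessment after chemoradiotherapy. This stands, and the numbers may be small. It does not settle the matter: the TME referral is not written for every patient who fails to complete six cycles, and the endpoint definitions exclude no one on this ground.
- **The patients are not invisible.** A reader of SAP 7.6 alone might infer that they would go uncounted. Tables 29 and 47 do not support that. What is missing is the link to the primary outcome.
- **The inflation is modest.** A reader might add irradiated successes on top of a 50% rate, p = 0.50 + f × s, and get 0.12 to 0.37 for f from 2% to 10%. That formula does not remove the irradiated patients from the group succeeding at 50%. It fits only if 50% is the rate over all patients with irradiated ones counted as failures, so that the others succeed at 0.50/0.90 = 55.6% when f = 10%. The documents do not state that premise.
- **Counting them is a defensible treatment-policy choice.** The primary objective and 8.3 concern avoiding TME, under a protocol that itself permits chemoradiotherapy. Recoding these patients as failures in the primary analysis also costs power. Both points stand. They argue for a paired rate rather than a compulsory change of primary endpoint.

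**Conclusion.** The definitional gap is real. The primary set and numerator have no radiotherapy condition, and the documents do not exclude TEMS/TAMIS after the permitted chemoradiotherapy. Such a patient with ypT0/T1good N0 and no TME would count as a success of chemotherapy without radiation.

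The size is uncertain and probably modest. With 2-10% irradiated and 50-68% success among them, against 50% in the others, P(promising) lies between 0.098 and 0.149. The lower end is no inflation at all. The switch rate is assumed; the success range is borrowed from the protocol's benchmark. If the observed count is close to 30, one such patient could still decide the verdict.

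The documents do not support saying that the protocol directs irradiated patients to TEMS/TAMIS, that the type I error is known to be inflated, or that the tables would hide these patients.

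**What to change.** 1. **Table 30:** add a row for pelvic radiotherapy before TEMS/TAMIS, split by organ preservation outcome.
2. **SAP 7.7.1:** beside the primary rate, and against the same threshold of 30 of 50, report a radiation-free organ preservation rate. Keep irradiated patients in the denominator and count them as non-successes.
3. **SAP 7.6:** replace the restriction to radiation before TME with radiation before any tumour excision.
4. **Reconcile** Protocol 7.1.1.1 note 3, 7.1.3.1 (including the undefined abbreviation in the neurological rows), 7.2 and 7.3 on what follows chemoradiotherapy. Which clinical route is right is for the sponsor to settle.

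The cost is small. SAP 2.2 places the final analysis on a database still to be locked, and the radiotherapy data already feed Tables 29 and 47. The downside is a little extra analysis and a second rate that may be lower than the first. If the sponsor instead makes the radiation-free rate primary, power at 65% falls from 0.80 to 0.745, 0.646 or 0.463 with 2%, 5% or 10% irradiated, and the SAP should say so.
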